9.1.2 Adverse Events of Medical Interest

Not applicable.

9.1.3 Expected Adverse Events

Based on pharmacologic action, the following AEs have been observed with Sym004:

- Electrolyte imbalances, including hypomagnesemia, hypocalcemia and hypokalemia
- Dermatological toxicities, acneiform rash, dry skin, fissuring of the skin and secondary skin infections
- Infusion reactions of variable severity

9.1.4 Serious Adverse Event

An SAE is an AE that meets one or more of the following criteria:

- Results in death
- Is life-threatening

NOTE: The term "life-threatening" in this definition refers to an event in which the patient is at immediate risk of death at the time of the event; it does not refer to an event which hypothetically might cause death if it was more severe

- Requires inpatient hospitalization or prolongation of existing hospitalization
- Results in persistent or significant disability/incapacity
- Is a congenital anomaly/birth defect
- Is medically important

NOTE: Medical and scientific judgment must be exercised in deciding whether an AE is believed to be "medically important". Medically important events may not be immediately life-threatening or result in death or hospitalization but may jeopardize the patient or may require intervention to prevent one of the other outcomes listed in the definition above.

In the case of deaths, the event(s) leading to the death should be recorded and reported as SAE(s) with the outcome "Fatal". The death itself will not be reported as an SAE, unless the cause of the death cannot be reported (e.g. in case of unexplained or sudden death).

Events That Do Not Meet the Definition of a Serious Adverse Event

Elective surgery or other scheduled hospitalization periods that were planned before the patient was included in this trial are not to be recorded as SAEs, unless an outcome is considered serious.

Hospitalization for observation or convenience following the Sym004/FOLFIRI infusions without an SAE occurring should not be recorded as an SAE, e.g. if a patient is hospitalized merely for observation, or if a patient finalizes the infusion at a time of day requiring a convenience overnight stay in the hospital.

If procedures to support the treatment regimens require hospitalization they should not be recorded as SAEs. However, in cases where a procedure results in complications requiring/prolonging hospitalization this must be recorded and reported as an SAE.

9.2 Adverse Event Recording and Reporting Instructions

9.2.1 Adverse Event Recording Period

All AEs will be recorded from signing the informed consent. The recording period ends at the time of the 1M FUP Visit.

NOTE: Patients who sign the informed consent and are subsequently deemed to be screening failures will be followed for the occurrence of SAEs/AEs until it is determined they will not be participating in the trial.

The Investigator must record all directly observed AEs and all AEs spontaneously reported by the patient. A general, open-ended type of question should be used to elicit a response from the patient, such as, “Do you have any health problems?” or “Have you had any health problems since your last visit?”.

All AEs that occur in patients during the AE recording period must be recorded/entered on the AE section of the Case Report Form (CRF), whether or not the event is assessed as related to Sym004. If the AE is serious, the SAE report forms must also be completed and submitted (see [Section 9.3](#)).

9.2.2 Diagnosis

A diagnosis should be recorded if possible. If no diagnosis is available, signs and symptoms should be recorded instead.

9.2.3 Intensity

The Investigator will use CTCAE version 4.03 to describe the severity of an AE. If the severity of an AE is not specifically graded by the CTCAE guidance document, the Investigator should use the general definitions of Grades 1 to 5 as per the following, and use his/her best medical judgment to describe the severity of the AE:

- Grade 1: Mild
- Grade 2: Moderate
- Grade 3: Severe
- Grade 4: Life-threatening or disabling
- Grade 5: Death caused by the event

Changes in severity of AEs will be recorded.

Generally, an AE of CTCAE Grade 4 or 5 qualifies for SAE reporting to the Sponsor or designee. However, a laboratory abnormality of CTCAE Grade 4 does not need to be reported as an SAE, unless it meets one of the seriousness criteria in [Section 9.1.4](#).

9.2.4 Relationship to Investigational Medicinal Product/Sym004 and FOLFIRI

The Investigator must assess the AE as either related or not related to the IMP and/or FOLFIRI. Relatedness has to be assessed and recorded within the initial report (CRF and SAE report form).

The causal relationship is an assessment of whether or not the event is related to the use of the IMP and/or FOLFIRI. It is not an evaluation of whether or not the event could hypothetically occur in the investigational patient population.

The causal relationship of an AE to the IMP and/or FOLFIRI will be rated as follows:

Not Related: The AE is not related to the IMP and/or FOLFIRI, which means the event:

- Does not follow a reasonable temporal sequence from drug administration
- Is readily explained by the patient's clinical state or by other modes of therapy administered to the patient
- The AE is clearly NOT related to the IMP and/or FOLFIRI

Related: The AE is related to the IMP and/or FOLFIRI, which means the event:

- Follows a reasonable temporal sequence from drug administration
- Abates upon discontinuation of the IMP and/or FOLFIRI (de-challenge)
- Is confirmed by reappearance of the reaction on repeat exposure (re-challenge)
- Cannot be reasonably explained by the known characteristics of the patient's clinical state
- Is not likely to have been produced by the patient's clinical state or by other modes of therapy administered to the patient

9.2.5 Outcome

Outcome of the AE must be assessed by the Investigator utilizing one of the following terms:

- Recovered
- Recovered with sequelae (if recovered with sequelae, specify sequelae)
- Not recovered
- Fatal
- Unknown

Instructions for reporting changes in an ongoing AE during a patient's participation in the trial are provided in the instructions that accompany the AE CRF pages.

9.2.6 Follow-up of Adverse Events

All AEs should be followed until they are resolved or until the 1M FUP Visit, whichever comes first.

NOTE: Patients who sign Informed Consent and are subsequently deemed to be screening failures will be followed for the occurrence of SAEs/AEs until it is determined they will not be participating in the trial.

9.3 Serious Adverse Event Recording and Reporting

All SAEs occurring at any time after the informed consent has been signed and until the 1M FUP Visit, must be recorded on the SAE report form and recorded as an SAE in the CRF.

NOTE: Patients who sign the informed consent and are subsequently deemed to be screening failures will be followed for the occurrence of SAEs/AEs until it is determined they will not be participating in the trial.

In case of an SAE, the Investigator must, within 24 hours of first awareness of the event, report the SAE to the Sponsor or designee. Fax numbers and the e-mail address are stated in the SAE report form and the SAE report form instruction.

Timelines for reporting of SAEs and SAE follow-up information are shown in [Table 18](#).

Table 18 Timelines for Reporting Serious Adverse Events and Follow-up

Type of event	Initial Report		Follow-up Report	
	Time Frame	Document	Time Frame	Document
SAE	24 hours	SAE report form	24 hours	SAE report form

Abbreviation: SAE, Serious Adverse Event

SAEs, still ongoing after 1M FUP Visit, should be followed on a regular basis according to the Investigator's clinical judgment, until the event has been resolved or until the Investigator assesses it as chronic or stable. The Sponsor or designee will pursue sufficient information and will return to the trial sites for such information as deemed required.

If the Investigator becomes aware of an SAE that occurred after the 1M FUP Visit for the patient and finds it related to the IMP or trial conduct it must be recorded and reported to the Sponsor or designee as an SAE. SAEs occurring after the 1M FUP Visit for a patient will not be reported as an SAE in the CRF, i.e. the event will only be recorded in the safety database.

The Investigator should be aware of local reporting regulations to the Institutional Review Board (IRB)/Independent Ethics Committee (IEC). The Sponsor or designee will either supply the Investigator with the reports, which should be forwarded to the IRB/IEC, or report directly to the IRB/IEC depending on local regulations.

9.4 Safety Reporting to Health Authorities, Independent Ethics Committees/Institutional Review Boards and Investigators

The Sponsor will assess seriousness, causality and expectedness of SAE as reported by Investigator. Expectedness of the event is based on the Reference Safety Information contained within the IB. The Sponsor or designee is responsible for reporting all relevant safety information, including Suspected Unexpected Serious Adverse Reactions (SUSARs), New Safety Issues and annual Development Safety Update Reports, to the Health Authorities (HAs) and to the IRB/IEC concerned. Where applicable as per local requirements, the Investigator will inform the IRB/IEC of the SUSAR.

The Sponsor or designee will inform all Investigators concerned of relevant information about SUSARs.

SUSARs will be reported within 7 days if fatal or life-threatening, otherwise within 15 days.

9.5 Dose-Limiting Toxicities

9.5.1 Definition of Dose-Limiting Toxicities

A DLT is defined as any of the following toxicities that occur during the DLT observation period, if considered by the Investigator, and confirmed by the ISMC, to be related to Sym004 or the Sym004/FOLFIRI combination:

1. Grade 3 non-hematologic toxicity regardless of duration, with the exceptions of:
 - a. Grade 3 nausea, vomiting, diarrhea, or fatigue lasting ≤ 5 days with best supportive care
 - b. Grade 3 asymptomatic electrolyte abnormalities¹
2. Any Grade 4 non-hematologic toxicity
3. Neutropenia that is:
 - a. Grade 3 or 4, associated with fever (ANC < 1000 per mm^3 ; temperature $> 38.5^\circ\text{C}$), and requiring antibiotic therapy
 - b. Grade 4 and sustained (i.e., ANC < 500 per mm^3 , duration > 5 days)
4. Thrombocytopenia that is Grade 4 (platelets $< 25,000$ per mm^3)
5. Inability to complete Cycle 1 at the initial assigned doses of Sym004 and FOLFIRI due to \geq Grade 3 toxicity
6. Treatment delays > 2 weeks from the scheduled “next doses” due to \geq Grade 3 toxicity

¹ In addition to the scheduled ECGs (at screening and EOT), an ECG should be performed as soon as possible in the event of \geq Grade 3 hypomagnesemia, and as otherwise clinically indicated. Furthermore, in the event of QT prolongation, an ECG is to be performed prior to the next dose of Sym004. See [Section 7.2.5](#) for further details regarding procedures to address this expected AE.

[Section 12.1](#) outlines the responsibilities of the ISMC with respect to DLTs.

9.5.2 Observation Period for Dose-Limiting Toxicities

Throughout the dose-escalation phase, the decision to dose-escalate is based on close monitoring of safety during the observation period for DLTs, defined as Cycle 1, i.e. the initial 28 day period (± 2 days) from first treatment of Sym004 in combination with FOLFIRI.

A minimum of 2 infusions of Sym004 in combination with FOLFIRI (full doses) must have been administered for a patient to have completed and tolerated the DLT observation period.

9.5.3 Reporting of Dose-Limiting Toxicities

All presumed DLTs must be reported to the Sponsor or designee within 24 hours after the Investigator or designee have become aware of the event. In addition, serious DLTs must be reported in an expedited manner according to the procedure for SAEs, as outlined above.

9.6 Reporting of Infusion-related Reactions

The definition of an IRR is included in [Section 7.1.4.7](#).

All IRRs must be reported in the CRF as an AE with the term “Infusion-related Reaction” followed by a specification of symptoms (e.g. “Infusion-related Reaction with dyspnea and flushing”).

In addition, serious IRRs must be reported in an expedited manner according to the procedure for SAEs, as outlined above.

9.7 Pregnancy

If any trial patient becomes pregnant during the course of the trial, the patient must be discontinued from Sym004 and FOLFIRI immediately and the pregnancy must be reported to the Sponsor or designee according to the same timelines as an SAE. While pregnancy is not considered an AE, all pregnancies are tracked as SAEs within the safety database in order to follow-up on exposure to the fetus/infant.

Pregnancies reported in female partners of male trial patients must also be data-based; therefore, a pregnant partner must provide informed consent before information can be collected.

All pregnancies must be followed up every third month to determine outcome (including premature termination) and status of mother and child. Pregnancy complications and elective terminations for medical reasons must be reported as AEs or SAEs as appropriate (trial patients only). Elective terminations for non-medical reasons should not be reported as AEs. Spontaneous abortion must be reported as an SAE.

Any SAE occurring in association with a pregnancy brought to the Investigator's attention after the patient has completed the trial and considered by the Investigator as possibly related to the IMP, must be promptly reported to the Sponsor or designee.

All pregnancy information including follow-up information must be reported in a designated pregnancy form provided by the Sponsor or designee.

10 STATISTICS

10.1 Sample Size Determination

The primary endpoint of the dose-escalation phase is the occurrence of DLTs on each of the Sym004 dose levels given in combination with FOLFIRI. The number of enrolled patients will depend on the extent of observed DLTs independently in each cohort. Please, refer to [Section 7.1.4.2](#) and [7.1.4.3](#) for a description of planned dose levels and decision tree for dose-escalation. Based on a 3 + 3 design, it is planned to enroll between 9 and 18 patients during dose-escalation.

In the dose-expansion phase of the trial, the primary endpoint is confirmed objective antitumor response to the combination of Sym004 and FOLFIRI. The number of patients planned to be included in this part of the trial is 32-41 patients depending on the number of patients enrolled in the dose-escalation phase.

In a Phase III study of patients with CRC treated with a second line regimen including panitumumab plus FOLFIRI, the response rate reported was 35% or 36% ([21](#), [22](#)). In one phase II study of CRC patients treated with cetuximab plus FOLFIRI as a second line regimen, a response rate of 32% was observed ([23](#)). The results from these studies were utilized as references to consider an increment in response rate that would support further studies to evaluate the potential efficacy of the combination of Sym004 and FOLFIRI.

If between 32 and 41 patients are included in the dose-expansion phase of the trial, the lower 90% exact confidence bound of a 47% observed response rate is at least 32%.

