
Criteria for Evaluation
	
All assessments are repeated throughout the trial at protocol specified intervals, unless otherwise stated.
 
Safety Assessments
 
 • Medication survey • (Serious) Adverse Event ([S]AE) survey • DLT evaluation (dose escalation only) during Cycle 1 with a final assessment 14 (±2) days after the last dose of Cycle 1 or on the scheduled first day of Cycle 2, prior to dosing • Vital signs and body weight • Eastern Cooperative Oncology Group (ECOG) performance status • Physical Examination • Dermatological Examination • Electrocardiogram (ECG) • Safety blood samples • Urinalysis • Pregnancy test 
Disease Assessments
 
 • (Archival) tumor tissue sample is requested at Screening after confirmation of eligibility • Tumor marker evaluation • Disease status evaluation by Computed Tomography (CT) or Magnetic Resonance Imaging (MRI) 
Additional Assessments*
 
 • Pharmacokinetic (PK) Sampling* • Anti-Drug Antibody (ADA) Testing* • Biomarker blood and urine sample* 
*Omitted with Amendment 3

Statistical Methods and Sample Size Calculation
	
The primary endpoint of the dose-escalation phase is the occurrence of DLTs observed during Cycle 1 on each of the Sym004 dose levels given in combination with FOLFIRI. The number of enrolled patients will depend on the observed DLTs independently in each cohort. Based on a 3 + 3 design, it is planned to enroll between 9 and 18 patients during dose-escalation.

	
In the dose-expansion phase of the trial, the primary endpoint is confirmed objective antitumor response to the combination of Sym004 and FOLFIRI. The number of patients planned to be included in this part of the trial is 32-41 patients depending on the number of patients enrolled in the dose-escalation phase.
 
The planned number of patients to be enrolled is not based on a formal sample size calculation.

--	--

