7.1.4.2 Dose-Escalation Phase

During the dose-escalation phase of the trial, the following dose levels of Sym004 will potentially be evaluated in combination with FOLFIRI:

- Dose Level 1: Sym004 12 mg/kg + FOLFIRI
- Dose Level 2: Sym004 15 mg/kg + FOLFIRI
- Dose Level 3: Sym004 18 mg/kg + FOLFIRI

If the toxicity profile of Dose Level 1 indicates that this dose is not tolerated, successive lower dose levels will be explored:

- Dose Level -1: Sym004 9 mg/kg + FOLFIRI
- Dose Level -2: Sym004 9 mg/kg (loading dose) + FOLFIRI followed by 6 mg/kg + FOLFIRI
- Dose Level -3: Sym004 6 mg/kg + FOLFIRI

If Sym004 at 9 mg/kg + FOLFIRI (Dose-Level -1) has not exceeded the MTD and is well tolerated during Cycle 1, but overall tolerability is judged to be insufficient to accept this dose level as the RP2D, then Dose Level -2 may be explored.

If Sym004 at 9 mg/kg + FOLFIRI (Dose-Level -1) during Cycle 1 has not exceeded the MTD, but tolerability is judged to be insufficient to accept this dose level as the RP2D, then Dose-Level -3 may be explored.

If the toxicity profile of lower doses where mandatory diarrhea prophylaxis is utilized indicates that the dose is well tolerated, further evaluation of Dose Level 1, and potentially Dose Levels 2 and 3 may take place after approval by the ISMC.

Cohorts will be filled sequentially. Patients will be allocated to the next available treatment slot within the current or next cohort, as appropriate and depending on the ongoing observation of DLTs and other safety parameters.

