10.3.2 Dose Expansion Phase

The primary objective of the dose-expansion phase is to evaluate the antineoplastic effect of Sym004. This will be evaluated by confirmed OR (i.e. documented PR or CR).

Number and percentages of patients in the FAS with confirmed OR will be presented including corresponding 95% exact Confidence Intervals (CI).

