10.4.2 Efficacy Endpoints and Analyses

The following anti-tumor response endpoints will be measured

- Documented OR (dose-escalation)
- Duration of OR from time of first PR or CR to PD
- Changes in sum of diameters of target lesions from baseline to end of trial participation

- SD for > 4 months
- Time to documented PD, death, patient withdrawal or end of trial participation, whichever comes first

All secondary efficacy endpoint will be presented using the FAS.

Best overall response by RECIST v1.1 will be summarized by trial phase and dose cohort by means of counts and percentages for the categories CR, PR, SD, PD and NE.

Number and percentages of patients with documented OR in the dose-escalation phase will be presented including corresponding 95% exact CI. All documented ORs (dose-escalation and dose-expansion phase) will be listed including duration of OR.

Duration of SD is calculated from baseline till first measurement of PD. The number and percentages of patients with SD for more than 4 months will be presented by trial phase.

Time to documented PD, death, patient withdrawal or end of trial participation, whichever comes first, will be presented using Kaplan-Meier plots by trial phase. The median survival time including 95% CI.

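### Does the 90% bound used to support the expansion size conflict with the 95% interval planned for the same endpoint?

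*Protocol*

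**What the plan says.** Section 10.1 plans 32 to 41 patients for the expansion phase. The range is what remains of the total of 50 once escalation is complete: "Based on a 3 + 3 design, it is planned to enroll between 9 and 18 patients during dose-escalation". The section then cites second-line response rates from earlier studies: 35% or 36% for panitumumab plus FOLFIRI, and for cetuximab plus FOLFIRI "a response rate of 32% was observed". It offers them as reference points for judging an increment, and closes with the statement that, for 32 to 41 patients, "the lower 90% exact confidence bound of a 47% observed response rate is at least 32" percent. It does not say whether the bound is one-sided or the lower end of a two-sided interval.

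Section 10.3.2 sets the primary analysis of the expansion phase: "Number and percentages of patients in the FAS with confirmed OR will be presented including corresponding 95% exact Confidence Intervals (CI"). Section 10.4.2 uses the same level for response in the escalation phase ("Number and percentages of patients with documented OR in the dose-escalation phase will be presented including corresponding 95% exact CI") and for the time-to-event endpoint ("The median survival time including 95% CI").

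The synopsis, under statistical methods, says: "The planned number of patients to be enrolled is not based on a formal sample size calculation".

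**The concern.** The 90% level in 10.1 is the only one of its kind in section 10; every interval planned for reporting is at 95%. The 32% in the planning statement also equals the cetuximab plus FOLFIRI rate cited just before it. A reader could infer that the expansion size was chosen so that a 47% result would exclude 32%, and then find that the interval actually reported does not exclude it. If so, the size would be supported by a property that the planned analysis cannot show. The unstated sidedness adds to the doubt, because the two readings give bounds about 3 percentage points apart.

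**Working it through.** **Inputs.** Expansion n = 50 − 18 = 32 to 50 − 9 = 41 (10.1, with the total from 5.5). Observed rate 47%, claimed bound at least 32% (10.1). Reported interval 95% exact (10.3.2).

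**Formula.** The exact (Clopper-Pearson) lower limit for x responders in n is the a-quantile of a Beta(x, n − x + 1) distribution, with a = 0.10 for a one-sided 90% bound, 0.05 for a two-sided 90% interval and 0.025 for a two-sided 95% interval.

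**Step 1: the plan's own figure.** With x = 0.47n (fractional, so that the rate is exactly 47%):

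| n | one-sided 90% | two-sided 90% | two-sided 95% |
|---|---|---|---|
| 32 | 34.6% | 31.7% | 29.2% |
| 33 | 34.8% | 31.9% | 29.5% |
| 36 | 35.3% | 32.6% | 30.2% |
| 41 | 36.1% | 33.5% | 31.3% |

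Read as one-sided, the 10.1 claim holds at every n with room to spare. Read as two-sided, it holds from n = 34 (32.1%) upward, and at n = 32 and 33 it holds after rounding to a whole percent. The two-sided minimum of 31.7% rounds to the printed 32%, so this is the likelier source of the figure. Under neither reading is the sentence wrong by more than rounding.

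**Step 2: attainable counts.** Fractional responders cannot occur. The whole counts that round to 47% are:

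| x/n | rate | one-sided 90% | two-sided 90% | two-sided 95% |
|---|---|---|---|---|
| 15/32 | 46.9% | 34.5% | 31.5% | 29.1% |
| 16/34 | 47.1% | 35.0% | 32.2% | 29.8% |
| 17/36 | 47.2% | 35.5% | 32.8% | 30.4% |
| 18/38 | 47.4% | 36.0% | 33.3% | 31.0% |

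Taking the count nearest 47% at each n from 32 to 41, the 95% lower limit runs from 28.8% (16/35, a rate of 45.7%) to 31.5% (19/40, a rate of 47.5%). It is below 32% throughout.

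**Step 3: the size of the gap.** In the two tables the 95% limit lies 2.2 to 2.5 points below the two-sided 90% limit (for example 33.5 − 31.3 = 2.2 at n = 41, and 31.7 − 29.2 = 2.5 at n = 32). A 95% lower limit of at least 32% needs 17/32 (53.1%), 18/36 (50.0%) or 20/41 (48.8%). That is two responders more than 15/32, one more than 17/36, and one more than 19/41.

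**Step 4: what depends on the gap.** Section 10.1 attaches no null hypothesis, success threshold or go/no-go rule to 32%, and it cites 35% and 36% alongside it. Section 10.3.2 does not refer to 32% at all. Nothing in the plan compares the reported lower limit with a reference rate.

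**The case for a change.** The best case for a change is that both statements stand in the same document, concern the same endpoint and use different levels without explanation, so this is not a matter left to an unseen SAP. The figures support it: the 95% lower limit falls short of 32% at every planned n. On the two-sided reading, at least 32% is slightly overstated at n = 32 and 33. Amendment 3 marks 10.4.3 and 10.4.4 as omitted but not 10.1 or 10.3.2, and 10.6 still allows the sponsor to collect efficacy data it considers necessary. The cost would be one sentence.

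The arithmetic stands, and so does the remark that the sidedness could have been stated. The step from there to a contradiction does not. A planning illustration at 90% and a reported interval at 95% can both be true and both be carried out: 10.1 does not promise a 90% interval in the analysis, and 10.3.2 does not promise a limit above 32%. That 32% acts as a benchmark is inferred from two matching numbers. The missing omission labels do not revive an expansion phase that, under section 5.5, will not reach its planned size.

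**Conclusion.** No change is called for. The levels differ, and at about 47% observed the reported 95% lower limit would be roughly 29% to 31%, not 32%. But the 10.1 sentence is correct one-sided and correct to rounding two-sided, and 10.3.2 fixes the reported interval unambiguously. Harmonising the text would leave the estimate, the interval and any decision as they are.

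This rests on two features of the plan: no decision rule is tied to the 32% figure, and the size is expressly not based on a formal calculation. Had 10.1 made a lower limit above 32% the criterion for going further, the difference of one or two responders would have mattered. Amendment 3 removes what practical weight was left, since accrual has stopped and sections 2 and 4.1 withdraw the objectives. At most this is an editorial remark: anyone citing 10.1 should say which kind of 90% bound is meant, and should not read it as a statement about the 95% interval.
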